7 DOSE ADJUSTMENT AND SAFETY MANAGEMENT

7.1 Dose Level and Regimen

The dose level in trial is 3 mg/kg, q2w or q3w, intravenously infusion over 30 minutes (no less than 20 minutes and no more than 60 minutes, including a wash-out period), until progression of disease, unacceptable toxicity, withdrawal of informed consent or the end of study, whichever comes first.

The administration interval cannot be less than 12 days at the frequency of once every two weeks. The administration interval cannot be less than 18 days at the frequency of once every three weeks. Dosing 3 days post the intended date of administration will be considered as delayed dose. The subsequent time of administration will be calculated on the actual date of the previous dose.

7.2 Dose Modification

7.2.1 Criteria for dose modification

Dose modification is not allowed.

7.2.2 Criteria for dose delay

The dose should be delayed if the following conditions occur:

- Any \geq Grade 2 treatment-related non-cutaneous AE, except Grade 2 treatment-related fatigue or laboratory abnormalities;
- Any Grade 3 treatment-related cutaneous AE;
- Any Grade 3 treatment-related laboratory abnormalities, except Grade 3 abnormal amylase or lipase unrelated with the symptoms and clinical manifestations of pancreatitis;
- The administration will be delayed if the following AST or ALT abnormalities occurs:
 - AST and ALT at baseline are within normal range, and Grade 2 treatment-related adverse events occur ;
 - AST or ALT at baseline elevates no greater than Grade 1, and Grade 3 treatment-related adverse events occur;
 - AST or ALT at baseline elevates no greater than Grade 2, and treatment-related elevated AST or ALT reaches > 2 times the baseline or either AST or ALT reaches $> 8 \times \text{ULN}$ (whichever is lower).

- The administration needs to be delayed for any AE, laboratory examination abnormalities or complications, as judged by investigators;

Subjects who need delayed dose should be monitored every week, and the frequency of monitoring can be increased when clinically indicated. It is recommended to monitor liver function every three days, until the highest value of AST or ALT starts to decrease. When meeting the criteria for resumption of medication (see Section 7.2.3), the investigational drug can be resumed.

Tumor evaluation still needs to proceed for all the subjects as required in the protocol, regardless of dose delay.

7.2.3 Criteria for dose resumption

When treatment-related AEs recover to \leq Grade 1 or baseline level, the dose can be resumed, except the following:

- The therapy can be resumed for the subjects with Grade 2 fatigue that has not been recovered;
- The therapy can be continued for Grade 2 cutaneous AE;
- For subjects with AST, ALT or TBIL Grade 1 elevation at baseline who delay SHR-1210 for reasons other than treatment-related hepatic AE, the therapy can be resumed in the presence of AST, ALT or TBIL Grade 2 elevations;
- For subjects who delay the dose for treatment-related AST, ALT or TBIL elevation, when these parameters are recovered to baseline CTCAE Grade or normal (see Section 7.2.4) and have not reached the criteria for permanent discontinuation of the treatment, the investigational drugs can be resumed;
- In the case that the treatment-related endocrine disorder can be sufficiently controlled only with hormone replacement at physiological dose, the treatment can be resumed.

The study medication is allowed to be delayed for up to 6 weeks, as calculated from the last dose. If the subject still does not reach the criteria for dose resumption after delay for 6 weeks, the study treatment need to be discontinued permanently, except the exceptions mentioned in Section 7.2.4. The guideline on management of adverse reactions is seen in Appendix 4 in detail.

7.2.4 Criteria for permanent treatment discontinuation

The study medication must be discontinued permanently when the following conditions occur:

- Any Grade 2 treatment-related uveitis, ophthalmodynia, and blurred vision, that has no response to local therapy and is not recovered to Grade 1 after delayed dose; or the above AE requiring systemic therapy.

- Any Grade 3 treatment-related non-cutaneous AE, lasting for > 7 days, except the following:
 - When any Grade 3 treatment-related uveitis, pneumonia, bronchospasm, hypersensitivity, or infusion reaction occurs, the study treatment must be terminated;
 - In case the Grade 3 treatment-related endocrine disorder can be sufficiently controlled only with hormone replacement therapy at physiological dose, the treatment does not need to be terminated;
 - The treatment does not need to be terminated for Grade 3 treatment-related laboratory abnormality, however, the study medication must be terminated for Grade 3 thrombocytopenia > 7 days or related with hemorrhage.
- Hepatotoxicity meeting the following:
 - AST or ALT > 10 times of ULN for over two weeks;
 - ALT or AST > 15 × ULN;
 - TBIL > 8 times of ULN for subjects with elevated TBIL at baseline, > 5 times of ULN for subjects with normal TBIL at baseline;
- Any Grade 4 treatment-related AE or abnormal laboratory examination, except the following:
 - Grade 4 granulocyte decrease lasts less than 7 days;
 - Grade 4 lymphopenia or leukopenia;
 - Isolated Grade 4 elevated amylase or lipase, without symptoms or clinical manifestations of pancreatitis. The sponsor needs to be informed in case of Grade 4 elevated amylase or lipase occurs;
 - Isolated Grade 4 electrolyte imbalance/abnormality without clinical sequela that could be corrected through supplement/appropriate management within 72 hours after occurrence;
 - Grade 4 treatment-related endocrine disorder that can be sufficiently controlled only with hormone replacement therapy at physiological dose, the treatment does not need to be terminated.

- The study treatment must be terminated in case dose delay > 6 weeks is required, except the following:
 - After the use of cortisol for management of treatment-related AEs, the study medication is allowed to be delayed for > 6 weeks due to the need for dose tapering. Discussion with the sponsor must be made before resuming the dose. During the dose delay, the tumor assessment should continue as required by the protocol. Safety visits and laboratory tests should also be performed at the original frequency (at least once every 6 weeks, window period \pm 7 days) or more frequently when clinically indicated;
 - The dose delay for > 6 weeks due to non-related reasons must be discussed with the sponsor prior to resuming administration. During dose delay, the tumor evaluation should still proceed as required in the protocol. Safety visits and laboratory examinations should also be performed at the original frequency (at least once every 6 weeks, window period \pm 7 days), or more frequently when clinically indicated;
- Clinical AE, laboratory abnormality, or complications may bring major risk to subjects who continue taking the study medication, as judged by investigators.
- Progression of disease evaluated by investigators in accordance with RECIST v1.1 (unless the subject meets the criteria in Section 3.2.4).

Even though the study medication is terminated, subjects must continue to perform tumor evaluation as required in the protocol.

7.3 Safety Management of Immuno-Oncology Drugs

7.3.1 Rules for safety management of immuno-oncology drugs

The AEs induced by Immuno-Oncology (I-O) drugs vary from other types of anti-cancer drugs, the severity and duration are special. SHR-1210 belongs to this type of drugs, thus it is required to achieve early identification and management of the AE induced by it, in order to reduce the incidence of serious toxicities. The investigator may refer to the rules for safety management of similar products in overseas markets to facilitate evaluation and management of I-O treatment-related AEs occurring in the following systems:

- Gastrointestinal tract
- Lung
- liver

- Endocrine
- Skin

Rules for safety management are provided in Appendix 4 in detail.

7.3.2 Rules for management on hepatic adverse events

Below are suggestions on management of hepatic AEs during the treatment period of this study:

- The criteria on dose delay resulted from hepatic AE are listed in Appendix 4. If the dose is delayed for 3–5 days and AST or ALT level is not improved but even exacerbated, cortisol, i.e., methylprednisolone 0.5–2 mg/kg/day or equivalent oral drugs will be given.
- In case of AST or ALT > 8 times of ULN, cortisol, i.e., methylprednisolone 0.5–2 mg/kg/day or equivalent oral drug will be given immediately.
- The sponsor must be informed within 24 hours when cortisol treatment starts. At the same time, a gastroenterology consultation is advised.
- If AST or ALT level is not improved but even exacerbated 3–5 days after the start of corticosteroids treatment, it must be discussed with the sponsor, and other immunosuppressants may need to be added, such as mycophenolate 1g BID.
- Once AST or ALT is decreased by CTCAE Grade, the dose can be decreased gradually in no less than one month.

The study medication can be resumed when AST or ALT is recovered to baseline level, unless the criteria on permanent discontinuation is reached.

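### The closing resumption sentence in Protocol 7.3.2 sets no bilirubin recovery condition and so contradicts 7.2.3 after a hold for treatment-related transaminase and bilirubin elevation

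*Protocol*

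**What the plan says.** Four places in the Protocol bear on when dosing may restart after a liver hold.

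- **7.3.2 (management of hepatic adverse events).** The section is introduced as suggestions, although its heading calls them rules. It ends: "The study medication can be resumed when AST or ALT is recovered to baseline level, unless the criteria on permanent discontinuation is reached". Bilirubin is not named.
- **7.2.2 (dose delay).** It sends the reader to 7.2.3: "When meeting the criteria for resumption of medication (see Section 7.2.3), the investigational drug can be resumed". Its general trigger for non-cutaneous events of Grade 2 or higher carries an exemption, "except Grade 2 treatment-related fatigue or laboratory abnormalities". A separate trigger delays dosing for "Any Grade 3 treatment-related laboratory abnormalities", apart from certain amylase or lipase findings.
- **7.2.3 (dose resumption).** The lead-in requires treatment-related events to be at or below "Grade 1 or baseline level, the dose can be resumed, except the following". One bullet covers subjects held for treatment-related AST, ALT or TBIL elevation and allows resumption "when these parameters are recovered to baseline CTCAE Grade or normal (see Section 7.2.4"), provided no permanent-stop criterion is reached. Another bullet covers subjects with Grade 1 elevation at baseline who were held "for reasons other than treatment-related hepatic AE, the therapy can be resumed in the presence of AST, ALT or TBIL Grade 2 elevations".
- **7.2.4 (permanent discontinuation).** The bilirubin stop limits are "> 5 times of ULN for subjects with normal TBIL at baseline", and above 8 x ULN where baseline TBIL was elevated.

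In addition, 6.6.2 states as a general principle for immune-related events that resumption can be considered at Grade 1 or below. The Grade 2 row of Table 5 says the same.

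**The concern.** A subject may be held because transaminases and bilirubin rose together on treatment. If the transaminases recover first, the site must decide whether to re-dose while bilirubin is still raised. An investigator managing the event from 7.3.2 finds the steroid steps, a pointer to Appendix 4 for the delay criteria, and a closing resumption sentence that looks complete. That sentence can be satisfied with bilirubin still at Grade 2. An investigator who turns to 7.2.3 finds that the dose may not be given.

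What is at stake is consistent handling of one liver-safety decision across sites. No effect on an endpoint or on the comparison of the two schedules is claimed.

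**Working it through.** The documents give no figure to reproduce. The check applies each rule to one defined case.

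**Case.** Dosing was held for treatment-related AST/ALT and TBIL elevation. AST and ALT are now back at baseline. TBIL is still above Grade 1 and above its own baseline grade. No 7.2.4 criterion is met.

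| Rule | Condition | Result |
|---|---|---|
| 7.3.2, closing sentence | AST or ALT at baseline, no permanent-stop criterion | Re-dose permitted |
| 7.2.3, lead-in | Event at Grade 1 or below, or at baseline level | Not met |
| 7.2.3, hepatic bullet | AST, ALT and TBIL at baseline grade or normal | Not met |
| 7.2.3, Grade 2 allowance | Grade 1 elevation at baseline and a non-hepatic reason for delay | Does not apply |
| 6.6.2 and Table 5 (immune-related events) | Grade 1 or below | Not met at Grade 2 |

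Because TBIL is above both Grade 1 and its baseline grade, the 7.2.3 result does not depend on whether the hepatic bullet tightens or relaxes the lead-in.

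**Can the case arise?** Yes. The 7.2.4 stop limits are ceilings at 5 and 8 x ULN, not recovery levels, and 7.2.4 says a Grade 3 laboratory abnormality does not by itself end treatment. The visible Annex 4 hepatic footnote allows delay instead of discontinuation with AST/ALT up to 8 x ULN and bilirubin up to 5 x ULN. A subject on hold with raised bilirubin is therefore foreseen.

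**Size.** The documents do not print the CTCAE bilirubin bands. Assume that Grade 1 runs to 1.5 x ULN and Grade 2 to 3 x ULN.

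- *Normal baseline TBIL.* Values above 1.5 and up to 5 x ULN satisfy the 7.3.2 sentence and fail 7.2.3. The 7.2.2 Grade 3 laboratory delay removes values above 3 x ULN. What remains is above 1.5 and up to 3 x ULN.
- *Elevated baseline TBIL.* Inclusion criterion 9 caps TBIL at 1.5 x ULN, so baseline is at most Grade 1. The span before the Grade 3 delay is above 1.5 and up to 8 x ULN. The same delay again leaves above 1.5 and up to 3 x ULN.
- *Sensitivity.* If the Grade 1 ceiling were 2 x ULN, the remaining range would be above 2 and up to 3 x ULN. In general it is the Grade 2 band, whatever its limits.

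**Example.** Baseline TBIL is normal, transaminases have recovered and TBIL is 2.5 x ULN. Since 2.5 < 5, no stop limit is met. Since 1.5 < 2.5 ≤ 3, it is Grade 2, which the general 7.2.2 trigger exempts as a laboratory abnormality. The 7.3.2 sentence allows the dose and 7.2.3 does not.

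**The case against.** The strongest reply is that the governing rule can be identified. Section 7.2.2 names 7.2.3 for resumption, 7.2.3 is the section on that subject and has a bullet for exactly this hold, and 7.3.2 is advisory and permissive. On this view a permissive sentence among suggestions does not waive a criterion set elsewhere. Most of this stands, and it is why the severity is low. It does not remove the contradiction: no sentence gives 7.2.3 precedence, and 7.3.2 neither refers to 7.2.3 nor presents its closing sentence as partial.

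Three further points also limit the weight.

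- *Other rules agree with 7.2.3.* A reader might infer that nothing else in the Protocol would stop a Grade 2 re-dose. That is not so for immune-related events, where 6.6.2 and Table 5 both look for Grade 1 or below. Table 5 is offered for reference only, but 7.3.2 is also advisory.
- *Grade 2 bilirubin is not always a reason to hold.* The general 7.2.2 trigger exempts Grade 2 laboratory abnormalities and there is no separate bilirubin trigger. Section 7.2.3 also accepts Grade 2 TBIL after a non-hepatic delay when baseline was Grade 1. The point is therefore confined to re-dosing after a hepatic hold.
- *Safeguards exist.* Laboratory results are reviewed before each dose (3.2.2), and the investigator may delay for any abnormality (7.2.2). The sponsor is told within 24 hours when steroids start (7.3.2). Section 9.2.3 makes defined combined transaminase and bilirubin elevations reportable as SAEs, which reach the sponsor within 24 hours (9.2.6). Sponsor discussion before resuming is required for the permitted delays beyond 6 weeks (7.2.4). None of these sets a bilirubin level for resumption.

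The Annex 4 hepatic flowchart is not shown and may state a bilirubin condition. That cannot be checked or counted against the plan. Even a correct flowchart would leave the 7.3.2 sentence at odds with 7.2.3.

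**Conclusion.** The closing sentence of 7.3.2 is wrong as written: it states a re-dosing rule that contradicts 7.2.3 for a subject held for treatment-related AST/ALT and TBIL elevation. Severity is low. The contradiction itself needs no assumption about CTCAE cut-offs. Only its translation into above 1.5 and up to 3 x ULN does.

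Two stronger readings are tempting and are not supported. The first is that subjects could be re-dosed with bilirubin up to 5 or 8 x ULN. Those are the stop limits, and the 7.2.2 delay for Grade 3 laboratory abnormalities removes most of that span, so they do not measure the gap. The second is that 7.2.3 also leaves bilirubin out. It does not: the parameters its hepatic bullet refers back to include TBIL.

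The number of subjects affected is unknown.

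**What to change.** Replace the last sentence of 7.3.2 with a rule that study medication may resume only when the criteria of Section 7.2.3 are met and no permanent-discontinuation criterion of Section 7.2.4 is reached. Check the Annex 4 hepatic flowchart for consistency with that rule. Spelling out AST, ALT and TBIL in the 7.2.3 hepatic bullet is optional, since all three are already covered.

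The cost is one sentence and one check. Blood biochemistry, which includes TBIL, is already done within 72 hours before each dose, so no test or visit is added. The downside is that some subjects will be held longer than the 7.3.2 sentence alone would allow, and a few may reach the 6-week delay limit. Section 7.2.3 already requires both.

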8 EFFICACY EVALUATION

8.1 Primary Endpoints and Observation Method

- 1) 6-month survival rate (6-month OS%): defined as the percentage of non-death cases in the evaluable subjects from the start of the trial to 6 months.
- 2) Objective response rate (ORR):

Defined as objective tumor response evaluated based on RECIST v1.1, including CR and PR cases.

Definition of evaluable population: all the subjects meeting the following criteria, i.e., having received at least one dose of SHR-1210 treatment and at least one tumor evaluation after the start of study treatment. If the efficacy reaches CR or PR, subjects must receive repeated test for confirmation in no less than 4 weeks (28 days) after the first evaluation.

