8.2 Secondary Endpoints and Observation Method

- 1). Duration of response (DoR): defined as the time from the date of first record of objective response (CR or PR) to the first occurrence of progression or death.
- 2). Time to progression (TTP): defined as the time from the date of randomization to any documented radiological tumor progression.
- 3). Disease control rate (DCR): defined as the percentage of subjects with CR, PR and SD (≥ 6 weeks) in the evaluable population.
- 4). Progression-free survival (PFS): defined as the time from randomization to any documented radiological tumor progression or death.
- 5). Overall survival (OS): defined as the time from randomization to death from any cause.

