11.2 Analysis Populations

Full analysis set (FAS): an analysis set determined in accordance with intention-to-treat principle. All the subjects who are randomized and have documented at least one dose of investigational drug will be included in this analysis set. The full analysis set is the primary efficacy analysis set.

Per protocol set (PPS): one subset of full analysis set. The subjects with protocol violation which has important influence on efficacy will be excluded from this set. The list of subjects who are included or excluded from PPS needs to be determined through review by the sponsor and investigators prior to lock of database.

Safety analysis set (SS): all the subjects who are randomized and have documented at least one dose of investigational drug will be included in the safety analysis set.

PD-L1 analysis set: PD-L1 expression analysis set of this trial comprise of all the subjects who have been randomized and enrolled and have received at least one dose of the investigational drug, and have provided tumor biopsy samples.

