11.3.2 Efficacy analysis

The tumor evaluation will be performed by the investigators based on RECIST v1.1. This evaluation data will be based on following responding parameters: complete response (CR), partial response (PR), stable disease (SD), progression of disease (PD), and not evaluable (NE). All the efficacy analysis will be based on the full-analysis set.

The survival distribution of OS will be estimated based on Kaplan-Meier (KM) method, median OS and two-sided 95% confidential interval will be calculated. In addition, KM method will be used to estimate the probability of survival at different time points (at month 6/9/12), and the corresponding 95% confidential interval will be calculated. Moreover, the subgroup analysis of OS will be performed by the predefined factors, the analytical method will be based on the aforementioned method.

The survival distribution of time to progression (TTP) will be estimated based on Kaplan-Meier (KM) method, median TTP and two-sided 95% confidential interval will be calculated.

The survival distribution of progression-free survival (PFS) will be estimated based on Kaplan-Meier (KM) method, median PFS and two-sided 95% confidential interval will be calculated. Objective response rate (ORR) and disease control rate (DCR): Clopper-Pearson method will be used to calculate the 95% confidential interval of overall percentage.

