4.1.6. Overall survival (OS)

Defined as the period from first dose to death due to any reason. It will be censored if no death occurs.

Rules for OS censoring are as below:

- If death is not obtained, the date of censoring will be the date of the last follow-up who are known to be alive.
- If the subject withdraws from the study and the date of death is not obtained, the date of censoring will be the last date who are known to be alive.

4.1.7. 6/9/12-month overall survival rate

Defined as the survival rate at 6/9/12 months after the date of first dose, which will be based on the Kaplan-Meier estimate.

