5.4. Efficacy Analysis

The efficacy analysis will be performed separately by group and overall.

Efficacy analysis will be based on IRC-assessed data and investigator-assessed data, with the former as the primary analysis.

Based on the FAS, PPS, and ES, ORR and 95% CI will be calculated separately by group and overall. The CI will be calculated using the Clopper-Pearson method. In addition, the difference in ORR will be calculated between the two groups, and Wald method will be used to estimate the 95% CI of the difference, and the nominal P value will be calculated based on Pearson Chi-square test.

In addition, based on the FAS, Amit method will be used to analyze the discrepancy between IRC-assessed and investigator-assessed PD/non-PD, BOR, and CR/PR.

Based on the FAS and PPS, Kaplan-Meier method will be used to calculate the 6/9/12-month OS% and the corresponding 95% CIs will be calculated.

Based on the FAS, the secondary efficacy endpoint PFS (including the 6/9/12-month PFS rate), TTP, OS, and DoR will be analyzed using Kaplan-Meier method. TTR will be descriptively summarized. When applicable, the survival curve will be plotted by endpoints. For PFS, TTP, OS, and DoR, the hazard ratios between groups and their 95% CIs will be computed using the COX proportional hazards model and nominal P values will be calculated using the log-rank test.

For the secondary efficacy endpoint DCR, the same statistical method with ORR will be used for analysis based on the FAS, the PPS, and the ES.

The best overall response (BOR) will be summarized.

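### Protocol 8.1 defines co-primary 6-month survival as a simple percentage of evaluable subjects, in conflict with the full-analysis-set Kaplan-Meier analysis in Protocol 11.3.2 and the SAP; the time origin also differs

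*Protocol*

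**What the plan says.** Protocol 8.1 lists 6-month survival as the first primary endpoint, "defined as the percentage of non-death cases in the evaluable subjects from the start of the trial to 6 months". Lower in the same section, under the ORR item, the evaluable population is defined as subjects "having received at least one dose of SHR-1210 treatment and at least one tumor evaluation after the start of study treatment". The flow chart and Protocol 3.2.2 put the first on-treatment scan at week 8 (±7 days).

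Other sections say something different:

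- **Population.** Protocol 11.2: "The full analysis set is the primary efficacy analysis set". Protocol 11.3.2: "All the efficacy analysis will be based on the full-analysis set".
- **Estimator.** Protocol 11.3.2: "KM method will be used to estimate the probability of survival at different time points (at month 6/9/12"). SAP 4.1.7: "Defined as the survival rate at 6/9/12 months after the date of first dose, which will be based on the Kaplan-Meier estimate". SAP 5.4: "Based on the FAS and PPS, Kaplan-Meier method will be used to calculate the 6/9/12-month OS" rate. SAP Table 1 marks the OS rate for the FAS, the per-protocol set and the PD-L1 set, but not for the evaluable set.
- **Time origin.** Protocol 8.1 counts from the start of the trial, which is not defined. Protocol 8.2 has OS "defined as the time from randomization to death from any cause". SAP 4.1.6 and 4.1.7 count from first dose.

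SAP section 3 sets the pass mark: the lower limit of the overall 95% CI for the 6-month OS rate must exceed 70%.

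**The concern.** A survival rate should count every treated subject. A subject who dies before the first scan has had the event being measured. A denominator that requires a scan removes that subject and raises the observed rate. Section 8.1 also has no rule for subjects lost before month 6, whereas Kaplan-Meier with the censoring rules in SAP 4.1.6 deals with them.

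The rate is compared with a fixed bound, so its definition decides what passes. Protocol 5.0 contains two definitions of the same co-primary endpoint and neither document says which prevails. Protocol section 11 asks that the SAP be kept consistent with the protocol, so the SAP cannot simply be assumed to override 8.1.

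**Working it through.** **1. The plan's own figure.** Inputs (Protocol 11.1, SAP 2.3): 80% against 70%, one-sided 0.025, 90% power, 200 subjects, 220 with drop-out. Using an exact binomial with the Clopper-Pearson lower limit, n = 200 passes with at least 153 survivors, with type I error 0.0249 and power 90.6%. The 200 is reproduced, and 200 × 1.10 = 220. The drop-out allowance for OS is 10%; the 80% evaluable share is applied to ORR only. The sizing therefore does not plan OS in scanned subjects.

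**2. Reference case.** All 220 in the denominator: pass with at least 168 survivors. At true 70%, P(lower limit > 70%) = 0.022.

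**3. Section 8.1 followed literally, only unscanned deaths removed.** Assumptions not in the documents: true 6-month OS 70%, a simple percentage with a Clopper-Pearson limit, no losses, n rounded. If a share m of the 220 dies unscanned by month 6, the observed rate is 0.70/(1 − m) on n = 220(1 − m).

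Under constant hazard, λ = −ln(0.70)/6 = 0.0594 per month. Week 8 is 56/30.44 = 1.84 months, so the share dead by then is 1 − exp(−0.0594 × 1.84) = 0.104, about 23 subjects.

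| Unscanned deaths removed | n | Rate read | P(lower limit > 70%) |
|---|---|---|---|
| None | 220 | 0.700 | 0.022 |
| 3% of subjects | 213 | 0.722 | 0.09 |
| 5% of subjects | 209 | 0.737 | 0.19 |
| 7% of subjects | 205 | 0.753 | 0.37 |
| A quarter of deaths before week 8 | 214 | 0.719 | 0.07 |
| Half of deaths before week 8 | 209 | 0.738 | 0.21 |
| All deaths before week 8 | 197 | 0.781 | 0.72 |

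The last row is 0.61 if the first scan is at week 7 (n = 200) and 0.81 if at week 9 (n = 195).

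**4. Living unscanned subjects also removed.** Borrow the 80% evaluable share from the ORR sizing: n = 220 × 0.80 = 176, pass with at least 136. If a proportion q of the 20% without a scan dies by month 6, the rate among the rest is [0.70 − 0.20(1 − q)]/0.80.

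| q | Rate read | P(lower limit > 70%) |
|---|---|---|
| 50% | 0.750 | 0.27 |
| 40% | 0.725 | 0.09 |
| 30% | 0.700 | 0.020 |
| 25% | 0.688 | 0.008 |

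At q = 30% there is no bias; below that it reverses. Even without bias, power at a true 80% falls from 92.2% (220) to 84.1% (176).

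**5. Losses before month 6.** Assume 10% are lost by month 6, with exponential times. A true 70% then reads 71.4% if losses count as non-deaths and 68.8% if they are left out. With no censoring, the percentage and Kaplan-Meier agree in the same population.

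**6. Time origin.** Dosing follows randomization within 3 days (Protocol 3.2.2). The shift is about 0.70 × [1 − exp(−0.0594 × 3/30.44)] = 0.0041, or 0.4 points; at a true 80% it is 0.3 points. The undefined origin in 8.1 cannot be sized.

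**The case against.** The best defence is that the analysis is already settled. Protocol 11.2, Protocol 11.3.2 and the SAP all point to Kaplan-Meier on the FAS, and the pass mark sits in the same SAP that defines the rate that way. The word in 8.1 may be loose: the formal definition is printed under ORR, DCR in Protocol 8.2 uses the defined term while the survival item uses a slightly different one, and SAP 5.2.2 speaks of evaluable subjects for demographics, where no scan is implied. The sizing agrees with this reading. The SAP revision table also records the move to first dose as deliberate.

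The 0.72 is also an extreme case. It needs a constant hazard from day 1, although entry requires a life expectancy of at least 12 weeks and ECOG 0–1, and it needs no unscheduled scan before an early death. If the hazard before week 8 were half the later one (an assumption), the share dead by week 8 would be 6.3%. The probability would then be 0.28 with all those deaths unscanned (n = 206) and 0.09 with half of them unscanned (n = 213).

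Much of this stands. A drafting slip is plausible, the bias depends on 8.1 being followed, and neither its size nor its direction is fixed by the documents. What does not stand is that the conflict is therefore resolved. Section 8.1 is where the endpoint is defined, item 1 uses the word, and the protocol offers no other meaning for it. The SAP's change of origin leaves Protocol 8.1 and 8.2 unaltered.

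**Conclusion.** The concern holds. Protocol 8.1 conflicts with Protocol 11.2 and 11.3.2 and with the SAP on the population and estimator of a co-primary endpoint, and three time origins are in force. The population matters most, because it can remove early deaths from a survival rate tested against a fixed 70% bound. The estimator matters only through censoring, and the gap between randomization and first dose is immaterial.

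If the FAS Kaplan-Meier analysis is run, there is no bias, and the 200 and 220 stand. If 8.1 were run at a true 70%, the false-success probability in the scenarios worked here goes from 0.008 to 0.81, against 0.022 with everyone counted; where it falls depends on how many unscanned subjects die. This should be corrected, but it does not undermine the planned analysis. Confidence is high in the textual conflict; the size of any bias is conditional.

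**What to change.** Replace the sentence in Protocol 8.1 with: the 6-month OS rate is the Kaplan-Meier estimate of survival at 6 months in the FAS, with subjects not known to have died censored at the date last known alive.

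State one time origin for survival and use it in Protocol 8.1, Protocol 8.2 (now randomization) and SAP 4.1.6–4.1.7 (now first dose). Confine the evaluable population to supportive ORR and DCR analyses, as SAP Table 1 already does with its evaluable set.

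The cost is one sentence in 8.1, with the time origin and the evaluable wording aligned. No new data, no new analysis and no change to the sample size are needed.
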